12.9.1 Data Guardianship

The data collected will be managed according to the study specific Sponsor Data Management Plan through the life cycle of the study and any specified data retention periods (see section 12.9.5). The participant and/or individuals/or others, including Indigenous, geographic and demographic specific communities, groups, and interests in relation to data will be recognised. Furthermore, the participant and/or individuals, others, or groups may be involved in the governance of their data. Data collected will also be subject to local data management guidelines as specified by local IRB/EC.

During this study, data will be collected and stored in two formats to maintain the welfare, safety and privacy of subjects. Data will be collected and managed in the following formats:

Identifiable information

Identifiable information is any data that could identify subjects (e.g. name, date of birth, or address). This information is used to complete study specific documents that are held at study sites, and the following people may have access to a subject's identifiable information:

- Research team members, including study doctor(s) and Research Coordinator(s).
- Lab techs, ultrasound techs and staff at radiology providers where diagnostic tests and study procedures are performed – they will collect and report any screening and follow up tests.

	No.: CP 65324	REV. D
	TITLE: Mini S Feasibility Study Protocol	
	CLASS: CLINICAL PROTOCOL	

- Study monitor (an authorized representative of the Sponsor will be provided with access to review medical records to check the accuracy of the information).
- The Sponsor and its representatives, in the instance a compensation claim for study-related injury. Identifiable information is required in order to assess any such claims.
- The Sponsor, Ethics Committees, or government agencies from this country or overseas (e.g. United States Food and Drug Administration (US FDA)), if the study or site is audited. Audits are done to make sure that subjects are protected, the study is run properly, and the data collected is correct.
- A subject's doctors or physicians, if a study test gives an unexpected result (incidental finding) that could be important for managing or maintaining health. This allows appropriate follow-up to be arranged.

De-identified information

To make sure a subject's personal information is kept confidential, information that identifies subjects will not be included in any study information sent to the Sponsor. Instead, subjects will be identified by a unique study number, also known as a "code". The research team will keep a list linking a subject's code with their name, so that they can be identified by their coded data if needed. The following groups may have access to a subject's de-identified and coded information as this will be sent and stored overseas:

- The Sponsor, for the purposes of this study.
- People and companies working with or for the sponsor, for the purposes of this study (this may include approx. 15 people across 5 organizations; Sponsor, Core lab providers (where imaging analysis occurs), CEC, DSM, and the Contract Research Organization (CRO).
- Regulatory or other governmental agencies worldwide.

12.9.2 Case Report Forms

All required data for this study will be collected via cloud-based electronic data capture (EDC) system and entered in electronic Case Report Forms (eCRFs).

All data collected during the study will be de-identified. For this purpose, a unique study identifier will be assigned to each study subject. All information recorded on the electronic Case Report form (eCRF) about the subject will be recorded including the study identifier. The database will contain only the study identifier to identify the subject. The code with subject name and study number will be maintained by the Principal Investigator in a secured location. Subject names will not be released to Shockwave Medical at any stage of the study.

	No.: CP 65324	REV. D
	TITLE: Mini S Feasibility Study Protocol	
	CLASS: CLINICAL PROTOCOL	PAGE 52 OF 70

12.9.3 Transmission of Data

Required data will be recorded on the appropriate electronic Case Report Forms at the time of or as soon as possible after the subject visit. The eCRF and any requested supporting source documents (including medical imaging files and source information associated with adverse events) must be sent to Shockwave Medical (if applicable to local site regulations) and/or verified/retrieved from the Investigator during monitoring visits. Data sent to Shockwave Medical will be de-identified and done so utilizing a secure web-based system.

12.9.4 Data Queries

Any data discrepancies identified during data review or a monitoring visit will be queried by Shockwave Medical or its designee and must be resolved by the investigational site staff and Investigator in a timely manner.

Data audits may be performed by Shockwave Medical or its designee for quality assurance of data handling. Any discrepancies will be queried by Shockwave Medical or its designee and must be resolved by the investigational site staff and Investigator in a timely manner, particularly during those times data is being prepared for CEC safety reviews and reports required by the regulatory authorities.

12.9.5 Data Retention

Shockwave Medical will retain all study data received for a period of two (2) years after the investigation is completed or terminated, or two (2) years after the records are no longer required to support the application to market the device (whichever date is later), or longer if required by applicable local regulations. The data will be retained in a secure, password protected database under the custodianship of the Sponsor and stored in the United States of America.

	No.: CP 65324	REV. D
	TITLE: Mini S Feasibility Study Protocol	
	CLASS: CLINICAL PROTOCOL	PAGE 53 OF 70

13.0 STUDY COMMITTEES

13.1 Clinical Events Committee (CEC)

To meet the ethical responsibilities and standards for research subjects, an independent Clinical Events Committee shall serve as forum for adjudication of certain pre-specified clinical event types, including SAEs, as described in the CEC charter.

The CEC will be managed by [REDACTED].

In order to enhance objectivity and reduce the potential for bias, the CEC shall be independent of the Study Sponsor as well as the study investigators.

The CEC is made up of clinicians with pertinent expertise who are not participants in the study and who do not have any other real or potential conflicts of interest. Members have expertise in peripheral endovascular procedures, are experienced in the conduct of controlled clinical trials and have knowledge of bioethics and integrity related to the duties and responsibilities to be performed.

The CEC is charged with the development of specific criteria used for the categorization of adverse events and clinical endpoints in the study. Criteria will be established for selected complications and clinical events. Events to be adjudicated include death, MAEs, revascularizations, and amputations. The CEC will also adjudicate relationship to the study device and study procedure according to the following classifications: definitely related, probably related, possibly related, unlikely related and not related.

At the onset of the study, the CEC will establish explicit rules outlining the minimum amount of data required and the algorithm followed in order to classify an event. The methodology for performing these responsibilities shall be developed and outlined in the CEC Charter. Operational provisions shall be established to minimize potential bias (i.e., CEC members shall be blinded to the clinical site to the extent possible during adverse event review and adjudication). The methodology for performing these responsibilities shall be developed and outlined in the CEC Charter. In addition, the CEC Charter will include the number of members, responsibilities, CEC meeting procedures, and meeting frequency.

13.2 Independent Data and Safety Monitor (DSM)

An independent Data and Safety Monitor (DSM) will be responsible for reviewing study data, monitoring for excessive occurrence of adverse events and making recommendations to Shockwave Medical regarding safety issues and risks to research participants as well as the continuing validity and scientific merit of the study. The DSM will make recommendations including (but not limited to) modification of the protocol, continuation/discontinuation of enrollment, and/or temporary suspension of enrollment in the trial. The DSM will be a physician with required training, experience and expertise in the field of peripheral endovascular procedures and in the conduct of clinical trials.

	No.: CP 65324	REV. D
	TITLE: Mini S Feasibility Study Protocol	
	CLASS: CLINICAL PROTOCOL	PAGE 54 OF 70

The independent DSM will conduct reviews of safety data in accordance with the protocol, local regulations where applicable, ICH E6: Good Clinical Practice (GCP) guidelines, and ISO14155:2020. At regular intervals during the course of the study, the DSM shall:

- Evaluate all adverse events with regard to interim results of the study for evidence of undue risk to research subjects and/or safety concerns.
- Provide recommendations regarding continuation/discontinuation of enrollment, and/or temporary suspension of enrollment due to safety concerns.
- Evaluate study progress with projections of recruitment and timelines for study milestones. This also includes evaluation of any significant trends of performance that may influence the safety or conduct of the study.
- Advise the Sponsor and other responsible parties on potential protocol-related concerns regarding procedures, definitions or endpoints, allowing timely notification of regulatory authority for protocol revisions.

In addition to regularly scheduled data reviews, the DSM will be notified immediately if any of the following events occur: any in-hospital death associated with the index procedure, any investigational device malfunction contributing to a serious adverse event, or failure to retrieve the investigational device.

	No.: CP 65324	REV. D
	TITLE: Mini S Feasibility Study Protocol	
	CLASS: CLINICAL PROTOCOL	PAGE 55 OF 70

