5.1 Safety Endpoints

The safety endpoints for this study include:

- **PRIMARY: Major Adverse Events (MAE)** at 30 days defined as a composite of:
 - Cardiovascular death
 - Clinically-driven target lesion revascularization (CD-TLR)
 - Unplanned target limb major amputation (above the ankle)
- **Serious angiographic complications** defined as flow-limiting dissection (\geq grade D), perforation, distal embolization, or acute vessel closure as assessed by the angiographic core lab.
- **MAE** at 6 and 12 months (as a composite and individual components)

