6.3 Type of Clinical Investigation

Per ISO 14155:2020 (Annex I, Section 1.4), the Mini S Feasibility study is considered to be an exploratory clinical investigation that does not have pre-specified primary hypotheses, but may be used to generate hypotheses to be confirmed in subsequent clinical investigations. Per ISO 14155:2020 (Annex I, Section 1.5), it is an early feasibility study in which the Mini S IVL catheter is being evaluated for the first time in human subjects.

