7.4 Schedule of Events and Evaluations

Table 1 lists the schedule of events and evaluations required for the study.

Table 1. Schedule of Events and Evaluations

Assessment	Screening / Baseline	Enrollment and Procedure	Discharge ¹	30 Days (-7/+14 days)	6 Months (180±30 days)	12 Months (365±30 days)	Pre-TLR
Eligibility	✓						
Informed Consent ²	✓						
Medical History	✓						
Physical Exam	✓			✓	✓	✓	
eGFR	✓						
Pregnancy Test	✓ ³						
Medications	✓		✓	✓	✓	✓	
ABI or TBI	✓ ⁴			✓	✓	✓	
Rutherford Category	✓			✓	✓	✓	
Angiogram		✓					✓ ⁵
DUS						✓	
Adverse Events		✓	✓	✓	✓	✓	✓
TLR = target limb revascularization; ABI = ankle-brachial index; TBI = toe-brachial index							
1. Within 12-24 hours post procedure or prior to hospital discharge, whichever occurs first							
2. Consent to be obtained within 30 days prior to procedure.							
3. Within seven (7) days of the procedure for women of child-bearing age.							
4. Within 60 days prior to procedure.							
5. Angiographic images acquired as standard of care prior to the TLR should be submitted to the core lab.							

	No.: CP 65324	REV. D
	TITLE: Mini S Feasibility Study Protocol	
	CLASS: CLINICAL PROTOCOL	PAGE 26 OF 70

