10.4.5 USADE Reporting Requirements

Investigators are required to submit a report of a USADE to the Study Sponsor as soon as possible, but not later than 2 business days after the Investigator first learns of the event. All USADEs should be reported to the IRB/EC in accordance with their local requirements.

	No.: CP 65324	REV. D
	TITLE: Mini S Feasibility Study Protocol	
	CLASS: CLINICAL PROTOCOL	

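### The three immediate DSM triggers in section 13.2 omit a 30-day death outside hospital, a 30-day major amputation and a USADE without malfunction, so independent advice on enrollment may come late

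*Protocol*

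**What the plan says.** Protocol section 13.2 gives the DSM the task of evaluating all adverse events at regular intervals and recommending whether enrollment should continue, pause or stop. It puts no number on those intervals. Outside the scheduled reviews, the DSM is told immediately of three events:

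- the first two: "any in-hospital death associated with the index procedure, any investigational device malfunction contributing to a serious adverse event";
- the third: "or failure to retrieve the investigational device".

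Other sections bear on how well that list fits the trial:

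- Sections 5.1 and 9.2.1 define the primary safety endpoint over 30 days. Its components are cardiovascular death, clinically driven target lesion revascularization (CD-TLR) and unplanned major amputation of the target limb.
- Note 1 to Table 1 (section 7.4) times the first post-procedure assessment: "Within 12-24 hours post procedure or prior to hospital discharge, whichever occurs first". The next visit is at 30 days.
- Sections 10.4.2 and 10.4.4 to 10.4.6 have sites report SAEs, SADEs and USADEs within 2 business days, with IRB/EC reporting under local rules. For USADEs, section 10.4.5 reads "Investigators are required to submit a report of a USADE to the Study Sponsor as soon as possible". The DSM is not named as a recipient.
- Section 12.5 obliges the sponsor to suspend the study while a suspected unacceptable risk is assessed.
- Section 6.3 states that "the Mini S IVL catheter is being evaluated for the first time in human subjects".

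**The concern.** The immediate-notice list does not match the trial's own safety endpoint. Of the three endpoint components, amputation and CD-TLR have no trigger of their own. Death has one only if it occurs in hospital and is linked to the procedure. An unanticipated serious device effect, arguably the most informative early signal for a new device, is not a trigger as such.

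This is not detail that a statistical analysis plan would supply. Section 13.2 states the list itself, has the DSM work in accordance with the protocol, and refers to no DSM charter; section 13.1, by contrast, refers the adjudication committee's methods to a charter. No DSM review is tied to a number of subjects treated. What is at stake is the timing of independent advice: the monitor appointed to say whether enrollment should go on may not be told of an event that bears on that question until the next scheduled review.

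**Working it through.** The protocol gives no figure to reproduce here. The check has three parts.

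**1. Events against triggers** (A = in-hospital death linked to the procedure, B = malfunction contributing to an SAE, C = failed retrieval):

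- Procedure-related death at home on, say, day 3, with no malfunction and the catheter retrieved: A no, B no, C no.
- Unplanned target-limb major amputation on, say, day 10, with no malfunction and the catheter retrieved: A no, B no, C no.
- USADE arising from use error or inadequate instructions: section 10.1.3 counts both as adverse device effects. Section 10.3.1 limits malfunction to a device that fails although used as instructed. Section 15.1 words malfunction differently, as an unexpected change to the device, which does not clearly cover these cases either. B is therefore not clearly met. C applies only if retrieval also fails, and A only if the event is a procedure-linked death in hospital.

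**2. Route to the DSM.** Each of these events reaches the sponsor within 2 business days. No section then requires the sponsor to pass the report to the DSM before the next scheduled review.

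**3. Scale.** Inputs:

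- Maximum enrollment 50 (section 6.5).
- Enrollment period 14 months. Section 6.6 prints the word six beside the figure 14. The total duration of 26 months less 12 months of follow-up gives 26 − 12 = 14, whereas 6 + 12 = 18 does not match 26. I use 14.
- Review interval: not stated; 1, 3 and 6 months are assumed.

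Average accrual = 50 / 14 = 3.57 subjects per month.

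Further subjects enrolled if the event falls just after a review = 3.57 × interval:

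- 1 month: 3.6, about 4 (3.6/50 = 7%)
- 3 months: 10.7, about 11 (10.7/50 = 21%)
- 6 months: 21.4, about 21 (21.4/50 = 43%)

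For comparison, the sponsor's route of 2 business days is 2 to 4 calendar days. At 30.4 days per month that is 3.57 × 2/30.4 = 0.23 to 3.57 × 4/30.4 = 0.47 subjects.

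**The case against.** The strongest reply is that the study is not unguarded. The sponsor hears of every one of these events within days, during which fewer than one further subject is expected. It must suspend on suspicion of unacceptable risk. Under section 12.5 an IRB/EC or regulator can itself suspend at its sites, which is stronger than recommending. Section 8.5 adds vigilance reporting and quality review of malfunctions and complaints. Nothing in section 13.2 forbids contacting the DSM sooner, and the breadth of ad hoc notices is partly a matter of preference. All of this stands. It rules out the inference that enrollment would simply continue, or that only the DSM could halt it. It does not put the information in front of the independent monitor.

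Other stronger readings that a reader might infer also fail:

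- That the list ends at death and malfunction. It does not: failed retrieval is the third trigger and could capture some USADEs without malfunction.
- That every death after discharge, and every amputation, is missed. A death on readmission may count as in-hospital, and an event to which a malfunction contributed falls under the second trigger. The clear gap is death outside hospital, and amputation, without malfunction or failed retrieval.
- That perforation illustrates a USADE outside the list. Section 5.1 already names perforation among the serious angiographic complications, so it may well be anticipated. Use error or inadequate instructions is the sounder example.
- That the in-hospital trigger covers only about 1 of the 30 days. Table 1 fixes when an assessment is done, not when subjects leave hospital.

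**Conclusion.** The point holds as a gap in the independent monitor's information, not as a contradiction in the protocol or proof of unsafe enrollment. Followed as written, section 13.2 lets a death outside hospital within 30 days, a 30-day unplanned major amputation or a USADE without malfunction wait for the next scheduled DSM review.

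The possible delay corresponds to up to about 4, 11 or 21 further subjects at review intervals of 1, 3 or 6 months. These are upper figures. They assume those intervals, full enrollment of 50 at a constant rate over 14 months, an event just after a review, no earlier contact with the DSM and no suspension by the sponsor, an IRB/EC or a regulator. None of the three should be read as the expected number.

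The change is cheap and worth making for a device at its first evaluation in humans.

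**What to change.** In section 13.2, keep the three existing triggers and add three more:

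- any death within 30 days of the index procedure;
- any unplanned target-limb major amputation within 30 days;
- any USADE, whether or not a malfunction occurred.

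State that the sponsor forwards to the DSM the report it already receives from the site.

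The triggers should be added, not substituted. Replacing the in-hospital death trigger with a 30-day one would lose a procedure-related in-hospital death after day 30. The addition leaves CD-TLR to the scheduled reviews; if that is intended, section 13.2 can say so.

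The cost is a short addition to section 13.2 and a forwarding step for reports already collected. The downside is a few extra ad hoc notices to the existing DSM, some of them for deaths that prove unrelated.

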14.0 ETHICAL and REGULATORY CONSIDERATIONS

14.1 Role of Shockwave Medical

As the Study Sponsor of this clinical study, Shockwave Medical has the overall responsibility for conduct of the study, including assurance that the study will be conducted according to ICH Good Clinical Practices (GCP), 21 CFR 812, 820, 50, 54, and 56, Declaration of Helsinki, applicable IRB/EC requirements, as well as any ISO 14155 and/or national requirements. In this study, Shockwave Medical will have certain direct responsibilities and may delegate other responsibilities to qualified consultants and/or contract research organizations. The specific federal regulations, international standards, and/or guidelines required to be followed should be outlined within the protocol. Sponsor will provide insurance for this study.

This protocol and any amendments will be submitted to each site's IRB/EC for formal approval of the study. All subjects considered for this study will be provided a consent form describing this study and providing sufficient information for them to make an informed decision about their participation.

14.2 Subject Confidentiality

As per the Data Management Section 12.9, subject confidentiality will be maintained throughout the clinical study. A unique subject identification code will be assigned and used to allow identification of all data reported for each subject.

Study data may be made available to third parties such as regulatory or auditing agencies (e.g., in the case of an audit) provided the data are treated confidentially and that the subject's privacy is guaranteed. The identity of a subject will never be disclosed in the event that study data are published. Data will not be provided to third party agencies that are not associated with the commercial or research operations of the Sponsor.

	No.: CP 65324	REV. D
	TITLE: Mini S Feasibility Study Protocol	
	CLASS: CLINICAL PROTOCOL	PAGE 56 OF 70

15.0 DEFINITIONS and ABBREVIATIONS

15.1 Study Definitions

Abrupt or Acute Closure: Angiographic documentation of significantly reduced flow due to mechanical dissection, thrombus, or severe vessel spasm in the treatment area.

Acute Limb Ischemia: A sudden decrease in limb perfusion that causes a potential threat to limb viability (manifested by ischemic rest pain, ischemic ulcers, and/or gangrene) in patients who present within two weeks of the acute event.

Adverse Device Effect (ADE): Adverse event related to the use of an investigational medical device.

Note: This definition includes adverse events resulting from insufficient or inadequate instructions for use, deployment, implantation, installation, or operation, or any malfunction of the investigational medical device.

Note: This definition includes any event resulting from use error or from intentional misuse of the investigational medical device.

Note: This includes "comparator" if the comparator is a medical device.

Adverse Event (AE): Untoward medical occurrence, unintended disease or injury, or untoward clinical signs (including abnormal laboratory findings) in subjects, users or other persons, whether or not related to the investigational medical device and whether anticipated or unanticipated.

Note: This definition includes events related to the investigational medical device or the comparator.

Note: This definition includes events related to the procedures involved.

Note: For users or other persons, this definition is restricted to events related to the use of investigational medical devices or comparators.

Amputation (major): Any requirement for amputation above the ankle.

Amputation (minor): Any requirement for amputation below the ankle.

Amputation, Unplanned: An amputation associated with the target limb that occurs between the index procedure and 30 days that was not previously planned as part of the overall treatment strategy.

Ankle-Brachial Index (ABI): The ratio of systolic blood pressure measured at the ankle to systolic blood pressure measured at the brachial artery.

Calcification Classification (PARC): Calcification will be assessed by the angiographic core lab according to the Peripheral Academic Research Consortium (PARC) definition [26].

PARC Degree of Lesion Calcification

Focal	Degree of lesion calcification
-------	--------------------------------

	No.: CP 65324	REV. D
	TITLE: Mini S Feasibility Study Protocol	
	CLASS: CLINICAL PROTOCOL	

Mild	<180° and greater than one-half of the total lesion length
Moderate	≥180° (both sides of vessel at same location) and less than one-half of the total lesion length
Severe	>180° (both sides of the vessel at the same location) and greater than one-half of the total lesion length

Clinical Events Committee (CEC): Committee responsible for establishing and implementing decision rules, definitions for the adjudication of clinical events using the data collected in the study, and for providing unbiased adjudication of clinical events.

Clinically Relevant Target Lesion Occlusion: Clinically relevant restenosis defined as the presence of a 50% or greater narrowing accompanied by a judgement of clinical relevance. Clinical relevance adjudicated by independent CEC based on worsening of Rutherford score, non-healing of wounds, ABI drop of ≥ 0.15 , TBI drop of ≥ 0.10 , each as compared to post-procedural outcomes, or absolute toe pressure ≤ 30 mmHg.

Closure, Abrupt: Occurrence of new (during the index procedure), persistent slow, reduced, or loss of flow within the target vessel that requires intervention other than the index or adjunct treatment. Abrupt closure may also be referred to as acute occlusion if there is a total loss of flow.

Closure, Subacute: Target lesion site occlusion that occurs after the index procedure is completed (e.g., the subject has left the treatment area) and within 30 days of procedure.

Critical Limb Ischemia: Clinical manifestation of peripheral arterial disease characterized by Rutherford Clinical Scale Category of 2-6. (For the purposes of this study, only subjects with Rutherford Clinical Scale Category of 2, 3, 4, and 5 are eligible for enrollment).

Data and Safety Monitor (DSM): Data and Safety Monitor will be responsible for reviewing study data, monitoring for excessive occurrence of adverse events and making recommendations to Shockwave Medical regarding safety issues and risks to research participants as well as the continuing validity and scientific merit of the study.

Death: (divided into 2 categories)

Cardiovascular death is death due to any of the following:

1. Acute myocardial infarction
2. Cardiac perforation/pericardial tamponade
3. Arrhythmia or conduction abnormality
4. Stroke within 30 days of the procedure or stroke suspected of being related to the procedure

	No.: CP 65324	REV. D
	TITLE: Mini S Feasibility Study Protocol	
	CLASS: CLINICAL PROTOCOL	

5. Death due to complication of the procedure, including bleeding, vascular repair, transfusion reaction, or bypass surgery
6. Any death for which a cardiovascular cause cannot be excluded

Non-cardiovascular death is a death not due to cardiovascular causes (as defined immediately above).

Device Deficiency: Inadequacy of a medical device with respect to its identity, quality, durability, reliability, usability, safety or performance.

Note: Device deficiencies include malfunctions, use errors, and inadequacy in the information supplied by the manufacturer including labelling.

Note: This definition includes device deficiencies related to the investigational medical device or the comparator.

Device Malfunction: A malfunction of a device is an unexpected change to the device that is contradictory to the Instructions for Use and may or may not affect device performance.

Dissection: Disruption of an arterial wall resulting in separation of the intimal layer. May or may not be flow limiting.

Dissection Classifications (National Heart, Lung and Blood Institute – NHLBI)

Type A: Minor radiolucent areas within the lumen without impairment of flow or persistent dye staining after contrast runoff.

Type B: Luminal flap that is radiolucent and runs parallel to the vessel wall with contrast injection but without impairment of flow or persistent dye staining after contrast runoff.

Type C: Contrast appears outside of the vessel lumen as an “extraluminal cap”, the staining appears even after contrast clears off the lumen.

Type D: Spiral radiolucent luminal filling defects, often persistent staining after contrast clears from the vessel.

Type E: New and persistent filling defects in the vessel lumen.

Type F: Lesions that progress to impaired flow or total occlusion.

Embolization, Distal: Any distal emboli confirmed by imaging considered to be related to the target lesion(s).

Embolization, Symptomatic: Clinical signs or symptoms of distal emboli detected in the treated limb distal to the treated lesion after the index procedure **or** noted angiographically and requiring mechanical or pharmacologic means to improve flow. This includes new abrupt occlusions or filling defects.

Intravascular Lithotripsy (IVL): Shockwave Medical's proprietary balloon angioplasty catheter including lithotripsy technology that creates pulsatile mechanical energy for disrupting calcified vascular plaque.

	No.: CP 65324	REV. D
	TITLE: Mini S Feasibility Study Protocol	
	CLASS: CLINICAL PROTOCOL	

Limb Ischemia: Deficient supply of oxygenated blood to the tissues in the limbs that is due to obstruction of the inflow of arterial blood characterized by pain and/or discoloration of the limb.

Lithotripsy: A medical procedure for disrupting calculus in the body.

Luminal Patency: Post-procedure residual stenosis <50% as determined by investigator visual assessment or quantitative analysis of the end of procedure angiogram.

Major Adverse Event (MAE): For the purposes of this study, the definition of Major Adverse Event(s) includes:

- cardiovascular death
- target lesion revascularization
- Unplanned target limb major amputation (above the ankle)

Perforation: Puncture of an arterial wall.

Restenosis: Reoccurrence of narrowing or blockage of target lesion.

Rutherford Classification of Critical Limb Ischemia: Clinical staging system for describing PAD. It includes 7 categories:

Grade	Category	Clinical Description
0	0	Asymptomatic
I	1	Mild claudication
	2	Moderate claudication
I	3	Severe claudication
	4	Ischemic rest pain
II	5	Ischemia ulceration not exceeding ulcer of the digits of the foot
III	6	Severe ischemic ulcers or frank gangrene
IV		

ACC/AHA/SCIA/SIR/SVM 2018 Appropriate Use Criteria for Peripheral Artery Intervention – Bailey et al. 2019)

Serious Adverse Device Effect (SADE): Adverse device effect that has resulted in any of the consequences characteristic of a serious adverse even.

Serious Adverse Event (SAE): Adverse event that led to any of the following:

- death,

	No.: CP 65324	REV. D
	TITLE: Mini S Feasibility Study Protocol	
	CLASS: CLINICAL PROTOCOL	

- serious deterioration in the health of the subject, user, or other persons as defined by one or more of the following:
 - a life-threatening illness or injury, or
 - a permanent impairment of a body structure or a body function including chronic diseases, or
 - in-patient or prolonged hospitalization, or
 - medical or surgical intervention to prevent life-threatening illness or injury, or permanent impairment to body structure or a body function,
 - foetal distress, foetal death, a congenital abnormality, or birth defect including physical or mental impairment.

Note: Planned hospitalization for a pre-existing condition, or a procedure required by the CIP, without serious deterioration in health, is not considered a serious adverse event.

Target Lesion Revascularization, Clinically-driven (TLR): A target lesion revascularization performed due to target lesion diameter stenosis $\geq 50\%$ and either evidence of clinical or functional ischemia (e.g., recurrent/progressive life-limiting intermittent claudication, claudication unresponsive to medical therapy, CLI) or recurrence of the clinical syndrome for which the initial procedure was performed. Clinically driven target lesion revascularization occurs in the absence of protocol directed surveillance ultrasound or angiography.

Target Vessel Revascularization, Clinically-driven (TVR), non-TLR: A target vessel revascularization performed due to non-target lesion diameter stenosis $\geq 50\%$ and either evidence of clinical or functional ischemia (e.g., recurrent/progressive life-limiting intermittent claudication, claudication unresponsive to medical therapy, CLI) or recurrence of the clinical syndrome for which the initial procedure was performed. Clinically driven target vessel revascularization occurs in the absence of protocol directed surveillance ultrasound or angiography.

Total Occlusion A 100% stenotic lesion as documented by angiographic absence of flow.

Toe Brachial Index (TBI): The ratio of systolic blood pressure measured at the toe to systolic blood pressure measured at the brachial artery.

Unanticipated Serious Adverse Device Effect (USADE): Serious adverse device effect which by its nature, incidence, severity or outcome has not been identified in the current risk assessment.

Note: Anticipated serious adverse device effect (ASADE) is an effect which by its nature, incidence, severity or outcome has been identified in the risk assessment.

Wound: Foot ulcer or gangrene. After debridement and/or minor amputation, a wound is characterized as a healed wound when it is completely epithelialized.

	No.: CP 65324	REV. D
	TITLE: Mini S Feasibility Study Protocol	
	CLASS: CLINICAL PROTOCOL	

